4.1 Hypothesis

Our central hypothesis is that nipple stimulation with an electronic breast pump to induce labor increases spontaneous vaginal delivery, shortens duration of labor induction, improves patient-reported pain scores during labor, improves patient satisfaction and sense of self agency with the birthing process, and improve scores on the postpartum depression scale. We also hypothesize that participants assigned to nipple stimulation therapy during labor will be more likely to use breastfeeding as the sole source of nutrition at hospital discharge, which will be associated with improved maternal perception of milk supply, less severe newborn weight loss, and sustained breastfeeding for the recommended 6 months. Secondly, we hypothesize that intrapartum nipple stimulation will not increase fetal or neonatal morbidity outcomes. Last, by examining cost of care and health-related quality of life, we hypothesize that performing nipple stimulation therapy during labor will be more cost-effective than the comparator after considering their overall impact on labor and delivery, breastfeeding, and early infant nutrition and care in the first 6 months.

We also hypothesize that nipple stimulation therapy invokes the wide cascade of events that promote labor to a greater extent than IV oxytocin alone. We hypothesize that oxytocin in the plasma of patients performing nipple stimulation will rise less than among subjects receiving IV oxytocin at the time when the subject is first contracting regularly. We hypothesize that other proteins associated with labor (including but not limited to IL6, IL1beta, plasminogen activator inhibitor 1, C reactive protein, ICOS ligand, and ERP29 will rise more in the circulation of subjects receiving nipple stimulation therapy compared with IV oxytocin. We hypothesize that urinary metabolites of prostaglandin E2 and F2alpha will be higher in subjects receiving nipple stimulation therapy. We hypothesize that, on a systematic level, plasma changes among subjects partaking in nipple stimulation will differ from subjects receiving IV oxytocin. We hypothesize that nipple stimulation therapy will have earlier secretory activation as measured by milk sodium and conductivity) in the early days postpartum, compared to individuals receiving IV oxytocin alone.

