practices/institutions. For the assessment of maximal newborn weight loss, it is standard hospital practice at study sites to regularly weigh each newborn during their birth hospitalization. Infants are weighed naked using a digital scale, and the weight is expressed in kilograms. At the study site, newborns are weighed at birth and then at least daily until day of discharge. The first weight measured after birth is usually performed after at least 6 hours post-birth. Weighing is typically discontinued if the newborn regains his or her birth weight prior to discharge. Infant birth weights are recorded in a standardized fashion in specific EMR flowsheets at study sites. The date and time of each weight are recorded which allows calculation of precise age.

- The following cost outcomes will be assessed: 1) cost of relevant care, and 2) health-related quality of life. Both outcomes will be measured for the mother-infant pair.
 - **Cost of care** will include direct medical cost, direct non-medical care, and indirect cost. Direct medical cost will encompass hospital facility costs and provider professional fees associated with relevant care (maternal labor and delivery hospitalization, newborn's initial birth hospitalization, and infant's postnatal pediatric visits). Direct non-medical cost will account for breast pump use at home, infant formula use, and transportation to relevant care. Indirect cost (i.e., maternal productivity loss) will measure participants' work loss in the postpartum period. As the project will span multiple years, we will use consumer price index to inflation adjust all cost estimates to a constant year U.S. dollars

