4. To assess subject-reported feelings of depression after childbirth, the Edinburgh Postnatal Depression Scale (EPDS) (32) will be administered at two different timepoints: (1) prior to initiating study intervention (to obtain baseline) and (2) at 4-12 weeks postpartum (ideally 6-8 weeks postpartum). The baseline EPDS will be reviewed, and the total score will be tabulated in real-time. The EPDS at 4-12 weeks postpartum will be completed by the subject online or with a certified study team member via telephone. A certified study team member will check daily (Monday-Friday) to review any completed online surveys and tabulate scores during these daily (Monday-Friday) reviews. If the EPDS at 4-12 weeks postpartum is completed with the subject via telephone, the total score will be tabulated at the conclusion of the telephone encounter. Any score ≥ 10 on either the baseline or 4-12 weeks postpartum EPDS will be reported to the subject's primary obstetric provider team as this is the threshold that suggests increased risk of depressive illness.
5. Prior to delivery hospitalization discharge, subjects will be asked if they had any intrapartum expression of colostrum or breast milk, the quantity (mL or ounces) expressed if known, whether they collected and stored it for their infant, and whether they fed it to their infant.
6. After delivery hospitalization discharge 2 weeks postpartum, all subjects will be administered the Perception of Inadequate Milk Supply (PIMS) (40) survey to assess their perception of their milk supply. In addition, the EQ-5D[™] and EQ-TIPS[™] surveys will be administered.
7. After delivery hospitalization discharge, between 4 to 12 weeks postpartum (ideally 6 to 8 weeks postpartum), all subjects will be contacted by text message, telephone, or by email (based on subject preference) to evaluate if they experienced any unanticipated outpatient or inpatient visits for them or their infants since delivery hospitalization discharge. Subjects will also be asked if they ever attempted to breastfeed postnatally.
8. Among subjects who state they attempted to breastfeed at least once postnatally; these subjects will be administered the Maternal Breastfeeding Evaluation Scale (MBES) (33) between 4 to 12 weeks postpartum (ideally 6 to 8 weeks postpartum) to assess their breastfeeding success. In addition, the EQ-5D[™] and EQ-TIPS[™] surveys will be administered.

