6.4.3.6 Health economic evaluation

To estimate difference in cost and difference in quality adjusted life years (QALY) between the intervention and comparator groups, we will use a generalized linear model (GLM) with log link and gamma distribution for cost (given skewness in cost data) and identity link and normal distribution for QALY. Explanatory variable will be an indicator for intervention (vs. comparator) group. All analyses will follow the intention to treat principle. As randomization will be stratified by study site and amniotic membrane status, we will test if they are associated with cost or QALY and decide whether to include them as covariates in analysis. Cost-effectiveness will be evaluated by calculating the incremental cost effectiveness ratio (ICER), defined as $\Delta C/\Delta E$ where ΔC denotes the estimated difference in cost between the intervention and comparator groups and ΔE reflects the estimated difference in QALY between the two groups. ICER informs the additional cost associated with the intervention for each additional QALY gained. We will use non-parametric bootstrap resampling to estimate 95% CI of ICER and produce a cost-effectiveness plane and cost-effectiveness acceptability curve. In special situations where the intervention leads to significantly lower cost and higher QALY, the intervention is considered the dominant strategy. In situations where there is no significant difference in QALY between the two groups, a comparison of cost will inform the cost-effectiveness of the intervention; and vice versa. Our primary cost-effectiveness analysis will examine costs and health effects up to 2 weeks postpartum. We will also conduct two secondary analyses by: 1) extending the time period to 6 months postpartum, and 2) calculating QALY using participants' EuroQol five dimensions (EQ-5D) visual analogue scale (VAS) rating as a utility score (with linear transformation to a 0 to 1 scale).

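### The cost definition ends maternal medical care at the delivery stay and leaves infant readmission unclear, although costs and QALYs are analysed to 2 weeks and 6 months

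*Protocol*

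**What the plan says.** Section 5.2.2 of the protocol defines the cost outcome. On scope it says: "Both outcomes will be measured for the mother-infant pair." Direct medical cost covers "hospital facility costs and provider professional fees associated with relevant care (maternal labor and delivery hospitalization", followed by "newborn's initial birth hospitalization, and infant's postnatal pediatric visits". The list has no opening such as 'for example'. Two further components follow: "Direct non-medical cost will account for breast pump use at home, infant formula use, and transportation to relevant care." and "Indirect cost (i.e., maternal productivity loss) will measure participants' work loss in the postpartum period."

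Section 6.4.3.6 sets the horizon: "Our primary cost-effectiveness analysis will examine costs and health effects up to 2 weeks postpartum." A secondary analysis extends it to 6 months. The same section lets the cost comparison alone inform cost-effectiveness if QALYs do not differ significantly between groups.

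Sections 6.2 and 6.3.1 schedule the maternal EQ-5D at baseline, in the postpartum stay, at 2 weeks, at 4 to 12 weeks and at 6 months. At 4 to 12 weeks, section 6.2 (item 7) also asks every woman about "any unanticipated outpatient or inpatient visits for them or their infants since delivery hospitalization discharge". Section 5.2.2 follows lactational mastitis to 12 weeks. Nothing in the protocol links these data to the cost outcome.

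**The concern.** An ICER is interpretable when its numerator and denominator cover the same events over the same period. Here the maternal effects run on after discharge and maternal medical costs stop there. If a woman is treated for mastitis or a wound infection, or is readmitted, her utility may fall and her lost work is costed, but the treatment is not.

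The intervention could plausibly change such care. The trial is sized for 10 percentage points more spontaneous vaginal deliveries (section 6.4.2), hence 10 points fewer operative ones, and it hypothesizes more breastfeeding (section 4.1). If post-discharge maternal care differs by arm, the cost difference is incomplete. The bootstrap interval in section 6.4.3.6 would not reveal this, because it resamples only the costs that were recorded.

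**Working it through.** **The plan's own figure.** Section 6.4.2 gives N = 988, 15% attrition at 2 weeks, two-sided alpha 0.05 and 90% power for a standardized difference of 0.22 in cost or QALY. Allocation is 1:1 (section 6.1.2).

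- Analysed per arm: 988 × 0.85 / 2 = 419.9.
- Power: Φ(0.22 × √(419.9/2) − 1.960) = Φ(3.188 − 1.960) = 0.890.
- Difference detectable at 90% power: (1.960 + 1.282) × √(2/419.9) = 0.224.

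The stated figure reproduces to rounding. The present point does not change it, because it concerns which costs enter the outcome and not the number of women.

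**What the definition counts after discharge.**

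| Consequence | Counted? | Source |
|---|---|---|
| Maternal health loss | Yes, as far as it shows at an EQ-5D assessment | 5.2.2, 6.3.1 |
| Maternal work loss | Yes | 5.2.2, indirect cost |
| Formula and home pump use | Yes | 5.2.2, non-medical cost |
| Infant pediatric visits | Yes | 5.2.2, direct medical cost |
| Infant readmission | Unclear | 5.2.2 names the initial stay and visits only |
| Maternal outpatient, emergency or inpatient treatment | No | not in the 5.2.2 list |
| Travel to that maternal treatment | Not as written, since transport is tied to relevant care | 5.2.2 |

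**Size of the omission.** For one type of event,

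omitted cost difference per pair = (rate with stimulation − rate with oxytocin) × unit cost.

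The protocol gives neither post-discharge rates nor unit costs, so every input here is an assumption:

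| Rate difference | $500 | $5,000 | $15,000 |
|---|---|---|---|
| −3 points | −$15 | −$150 | −$450 |
| −1 point | −$5 | −$50 | −$150 |
| 0 | $0 | $0 | $0 |
| +1 point | $5 | $50 | $150 |
| +3 points | $15 | $150 | $450 |

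**Sign.** Fewer operative births could mean less wound and infection care in the stimulation arm, and the omission would then understate its saving. More breastfeeding could mean more mastitis care, and the omission would then overstate it. The protocol does not say which dominates.

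**Horizon.** Mastitis is followed for 12 weeks, and the primary analysis covers only the first 2 of them. Post-discharge care has most time to accrue in the 6-month analysis.

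**The case against.** The strongest reply is that the scope was chosen. Section 4.1 frames the cost-effectiveness hypothesis as holding "after considering their overall impact on labor and delivery, breastfeeding, and early infant nutrition and care in the first 6 months". That wording does not name maternal care after discharge, and the 5.2.2 list fits it fairly well. This stands as far as it goes: the two sections do not contradict each other. It does not explain why maternal EQ-5D and work loss are counted after discharge while maternal treatment is not, and the protocol states no narrower costing perspective.

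Section 6.2 also says that economic costs will be assessed at 6 months, and costing detail is commonly left to an analysis plan. But that sentence sets a time point and does not widen the list, and it is the protocol that defines the outcome.

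Four stronger readings are tempting, and the protocol does not support them.

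1. A reader might infer that infant readmissions are excluded. The word 'initial' points that way, but section 6.2 itself speaks of inpatient visits, so pediatric visits could include them. The wording is ambiguous.
2. A reader might infer that costing is tilted toward formula savings. Home pump use, transportation and work loss are counted too, and the first is itself a cost of breastfeeding.
3. A reader might infer that the ICER is biased. That needs an arm difference in the omitted care, and it is not established.
4. A reader might attach a large ICER shift. With an assumed utility gain of 0.02 for both mother and infant, the 2-week gain is 2 × 0.02 × 14/365 = 0.00153 QALY, so $100 from any source moves the ratio by about $65,000 per QALY. That reflects the small denominator and does not show that $100 is missing. For a 10-point shift in delivery mode to produce a 1-point difference in readmission, readmission would have to be 0.01/0.10 = 10 points more common after operative birth. The protocol supports no such figure. Likewise, $100 equals the detectable 0.22 SD only if the cost SD is about 100/0.22 = $455, and the protocol gives no SD.

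**Conclusion.** The point holds in a limited form. Followed as written, section 5.2.2 leaves out the treatment cost of maternal events after discharge, while their effects on QALYs and work loss are counted, and it leaves infant readmission undefined. The cost difference is incomplete, and section 6.4.3.6 may rely on it alone. It is biased only if the omitted care differs between arms. The direction is unknown and the size cannot be derived from the protocol; the −$450 to +$450 range rests wholly on assumed inputs. The effect is probably small at 2 weeks and larger at 6 months. It touches one secondary objective. The primary outcome, randomization and sample size are unaffected. The change is worth making because it is cheap.

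**What to change.** In section 5.2.2, add maternal outpatient, emergency and inpatient care after discharge to the relevant care that is costed, and name infant readmission explicitly, over each analysis horizon. Then:

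- Add date and type of visit to the existing 4-to-12-week question, so that each event can be placed inside or outside the 2-week window.
- Check it against the medical record. The question covers only unanticipated visits.
- Repeat the question in the 6-month survey, which now lists only infant feeding, EQ-5D and EQ-TIPS.
- Assign unit costs, including for care at outside institutions.

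If the narrower scope is intended, state that perspective and justify it.

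The cost is protocol wording, two data fields, one repeated survey item, and some extra data entry and costing work. No additional participants or encounters are needed. Self-reported visits carry some recall error, and for women already past 6 months postpartum a new survey item comes too late, so the record and any answers already given must serve.

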5.3 Study Population

Pregnant women who are nulliparas with live gestations of 36 weeks and greater who are planned to receive (but have not yet received) exogenous oxytocin infusion for induction of labor. While pregnant women represent a vulnerable population, they represent the study population of interest.

5.3.1 Number of Participants

The sample size for the trial is based on the primary outcome of spontaneous vaginal delivery. Therefore, the sample size of $n=988$ (shared between Yale, Weill Cornell Medicine and Northwestern) is selected for this proposed study to detect a 10% absolute increase while accounting for an expected 5% attrition rate. We then estimate, on the basis of the sample size for the primary outcome, the power we will have to detect clinically significant differences in the secondary outcomes.

For the translational sub-study at Yale, we will seek consent to obtain plasma and urine from patients enrolled in the main study ($n=192$). In addition, plasma will be obtained from 48 patients in spontaneous labor.

For the milk collection sub-study at Yale and Weill Cornell Medicine, to detect a 10 mM difference in sodium concentration between the intrapartum nipple stimulation therapy group and the immediate synthetic oxytocin infusion group at 48 hours postpartum, with a standard deviation of 20 mM, 80% power, and a significance level of 0.05, a sample size of 32 participants per group is required. Accounting for an expected 30% dropout rate, we plan to recruit 46 participants per group.

5.3.2 Eligibility Criteria/Vulnerable Populations

We will use broad inclusion criteria to ensure generalizability of our results.

Inclusion criteria

- Age 18 years and older
- Nulliparous women (a prior pregnancy that ended at $<20^{0/7}$ weeks of gestation is acceptable)
- Gestational age $36^{0/7}$ weeks and greater at enrollment
- Singleton gestation (a multiple gestation reduced to a singleton, either spontaneously or therapeutically, before $14^{0/7}$ weeks of gestation is acceptable)
- Planned to undergo initiation of exogenous oxytocin infusion by their maternity care provider
- Cervix dilated <6 cm within one hour of enrollment (if membranes intact) OR ruptured membranes with less than 3 contractions in a 10-minute window averaged over 30 minutes prior to enrollment (regardless of cervical exam)

- Ability to give informed consent

Exclusion criteria

- Unable to understand English or Spanish
- Presence of tachysystole (defined as more than 5 contractions in 10 minutes averaged over 30 minutes), recurrent variable or late fetal decelerations, and bradycardia in the prior 30 minutes before enrollment
- Non-vertex presenting fetus at time of enrollment
- Planned for cesarean delivery or contraindication to labor by institutional policy (e.g., placenta previa, vasa previa, active genital herpes infection, previous transmural myomectomy)
- Multi-fetal gestation (e.g., twins, triplets, and higher-order multiples)
- Intrauterine fetal death
- Major fetal anomaly suspected prenatally (defined as a fetal anomaly with anticipated neonatal intensive care unit admission)
- Suspected alloimmunization (given the increased likelihood for anticipated neonatal intensive care unit admission)
- Known severe fetal growth restriction (estimated fetal weight <3rd percentile) or abnormal umbilical artery Doppler studies (given the increased likelihood for anticipated neonatal intensive care unit admission)
- HIV infection (nipple stimulation is not encouraged given the recommendation for these mothers not to breastfeed)
- Participation in another interventional study that influences management of labor and delivery or perinatal morbidity or mortality
- History of mastectomy or other contraindication to manual nipple stimulation or use of electronic breast pump
- Known allergic reactions to components of the electronic breast pump or to synthetic oxytocin intravenous solution
- Significantly impaired consciousness or executive function (e.g., intubated or sedated)

For collection of plasma and urine from patient participants in early spontaneous labor (defined as <6 cm dilated with intact membranes), inclusion criteria will be:

- Age 18 years and older
- Nulliparous

- Gestational age 36 0/7 and greater
- Singleton gestation
- Ability to give informed consent
- Presenting in early spontaneous labor defined as <6cm dilated with intact membranes.
- Patient and primary obstetric provider intend for patient to continue spontaneous labor

For collection of plasma and urine from patient participants in early spontaneous labor (defined as <6 cm dilated with intact membranes), exclusion criteria will be:

- Patient has performed nipple stimulation in the preceding 24 hours, received outpatient prostaglandin therapy, or had “membrane stripping” in the preceding 24 hours
- Patient is expected to have labor complications preventing continued spontaneous labor, such as arrest of dilation or fetal intolerance of labor

6 - Methods

6.1 Treatment

6.1.1 Intervention administration and schedule

Subjects will be encouraged to perform nipple stimulation with the aid of an electronic breast pump to promote standardization of the stimulation. The subject will be provided with a hospital-grade breast pump. The subject may choose to use their own personal non-hospital breast pump instead. Subjects can also alternatively choose to perform nipple stimulation by hand if they desire. Subjects will receive a 5-10 minute tutorial on either method by their labor nurse and supported by their labor nurse with the additional assistance of hospital lactation consultants if needed during their stimulation process. All labor nurses and hospital lactation consultations are educated on proper breast pump use.

6.1.2 Method of Assignment/Randomization

Enrolled subjects will be randomly assigned in a 1:1 ratio to both study groups. A web-based randomization sequence will be prepared using blocks of variable sizes, stratified by study site and amniotic membrane status (intact versus ruptured), and maintained centrally by the study statistician. The advantage of this method is that it provides a good probability of balance, and future assignments are unpredictable. A subject's group assignment will be obtained only after the subject is confirmed to continue to meet inclusion criteria, and a study number is entered and locked in using *REDCap* (Research Electronic Data Capture), an established, secure, web-based capture and management tool developed at Vanderbilt University. Although blinding of both subjects and their obstetrical clinicians would be ideal, blinding is clearly not possible in this trial. We will minimize systematic bias by applying the

same standard procedures for other labor and management strategies between groups at each study site. Further, the group assignment of subject will not be taken into account by trained study staff collecting maternal and neonatal outcomes. Importantly, the main study outcomes of spontaneous vaginal delivery and breastfeeding as the sole source of infant nutrition at hospital discharge are objective measures.

